9.3 POPULATIONS FOR ANALYSES

The analysis populations are defined in [Table 6](#).

Table 6 - Analyses population

Population	Description
Screened	All participants who sign the ICF
Randomized	The randomized population includes all participants with a treatment kit number allocated and recorded in the IRT database, and regardless of whether the treatment kit was used or not. Participants treated without being randomized will not be considered randomized and will not be included in any efficacy population.
Intent-to-treat (ITT)	All randomized participants analyzed according to the treatment group allocated by randomization.
Efficacy	The ITT population
Safety	All participants randomly assigned to IMP and who take at least 1 dose of study IMP. Participants will be analyzed according to the intervention they actually received. Randomized participants for whom it is unclear whether they took the study IMP will be included in the safety population as randomized. For participants who accidentally receive different treatment from the planned, the actual intervention allocation for as-treated analysis will be the dupilumab group. The PD analyses will be performed on the safety population.
Pharmacokinetic (PK)	The PK population includes all participants in the safety population with at least 1 non-missing result for functional dupilumab concentration in serum after first dose of the IMP. Participants will be analyzed according to the intervention actually received.
Antidrug antibody (ADA)	ADA population includes all participants in the safety population who have at least 1 non-missing ADA result after first dose of the IMP. Participants will be analyzed according to the intervention actually received.

Abbreviations: ADA = antidrug antibody; ICF = Informed consent form, IMP = investigational medicinal product; IRT = Interactive response technology; ITT = intent-to-treat; PD = Pharmacodynamic; PK = Pharmacokinetic.

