3 ANALYSIS POPULATIONS

The following populations for analyses are defined:

Table 3 - Populations for analyses

Population	Description
Screened	All participants who sign the ICF
Randomized	All participants from the screened population who have been allocated to a randomized intervention by IRT regardless of whether the treatment kit was used or not. Participants treated without being randomized will not be considered randomized and will not be included in any efficacy population.
Intent-to-treat (ITT)	All randomized participants analyzed according to the intervention group allocated by randomization.
Safety	All participants randomly assigned to study intervention and who take at least 1 dose of study intervention. Participants will be analyzed according to the intervention they actually received. Randomized participants for whom it is unclear whether they took the study medication will be included in the safety population as randomized. For participants who accidentally receive a different intervention from that which was planned, the actual intervention allocation for as-treated analysis will be the dupilumab group. The pharmacodynamic (PD) analyses will be performed on the safety population.
Pharmacokinetic (PK)	The PK population includes all participants in the safety population with at least one non-missing result for functional dupilumab concentration in serum after first dose of the study intervention. Participants will be analyzed according to the intervention actually received.
Anti-drug antibody (ADA)	ADA population includes all participants in the safety population who have at least one non-missing ADA result after first dose of the study intervention. Participants will be analyzed according to the intervention actually received.

Abbreviations: ITT = intent-to-treat, ADA = antidirug antibody; ICF = Informed consent form, IRT = Interactive response technology; PD = Pharmacodynamic, PK = Pharmacokinetic

Participants exposed to study intervention before or without being randomized will not be considered randomized and will not be included in any analysis population. The safety experience of these participants will be reported separately.

Randomized participants for whom it is unclear whether they took the study intervention will be considered as exposed and will be included in the safety population as randomized.

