For the efficacy assessment, the reference date for the derivation of relative days of events or findings will be the randomization day. If a participant receives IMP prior to the randomization by mistake, the reference date of efficacy assessment will be the date of the first IMP administration for that participant. For the primary analyses, all available values of scheduled measurements will be assigned to the appropriate visit window according to [Table 10](#). In the event of multiple measurements of the same test in the same window, the one closest to the targeted visit date will be used for the by-visit summary. If they are at the same number of days away from the target day, the latest one will be used.

Table 10 - Time window for efficacy variables

Visit	Target Day	Time windows for				
		Ice cube, UCT	Likert, NRS	ColdUAS, PGIS	PGIC	DLQI/CDLQI, ColdU-QoL, EQ-5D-5L, [REDACTED]
Visit 1	-28 to -14	<-14		<-14		
Visit 2 (Week 0)	1	-14-1-	<1-	-14-1-		<1-
Visit 3 (Week 12)	85	1+-126	1+-126	1+-126	1+-126	
Visit 4 (Week 24)	169	127-210	127-210	>126	>126	≥1+
Visit 5 (Week 36)	253	>210	>210			

1-: up to randomization and before 1st dose date/time; 1+: after randomization or 1st dose date/time

For the pharmacokinetics/pharmacodynamics variables summary, the reference date for the derivation of relative days of measurements will be the date of first IMP administration if the participant is treated with study intervention, or the randomization date if the participant is not treated. Pharmacokinetics/pharmacodynamics variables will be summarized by the analysis window defined in [Table 11](#) for the by visit descriptive analyses. All available values of measurements will be assigned to the appropriate visit window. In the event of multiple measurements of the same test in the same window, the one closest to the targeted visit date will be used for the by-visit summary. If they are at the same number of days away from the target day, the latest one will be used. For procedures planned on Visit 2, if it is done on the same date as the first IMP injection but the performance time is missing, it will belong to Visit 2 time window.

Table 11 - Time window for pharmacokinetics/pharmacodynamics variables

Visit	Target Day	Serum dupilumab, ADA, Total IgE	Basophil activation (optional)
Visit 1	-28 to -14		
Visit 2 (Week 0)	1	<1-	<1-
Visit 3 (Week 12)	85	1+-126	1+-126
Visit 4 (Week 24)	169	127-210	>126
Visit 5 (Week 36)	253	>210	

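### SAP Section 3 drops from every analysis population a participant dosed before being randomised, although SAP Table 3 and the protocol keep anyone allocated by IRT

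*SAP*

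**What the plan says.** SAP Table 3 puts into the Randomized population every screened participant given an allocation by the IRT, with no regard to kit use. The same row carries one exclusion: "Participants treated without being randomized will not be considered randomized and will not be included in any efficacy population". The ITT row then takes in everyone who was randomised: "All randomized participants analyzed according to the intervention group allocated by randomization". For the safety population the table's entry reads "All participants randomly assigned to study intervention and who take at least 1 dose of study intervention", and the PK and ADA populations are subsets of it. None of these definitions depends on when the first dose was taken.

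Protocol Section 9.3, Table 6, agrees. Randomized means having a kit number allocated and recorded in the IRT database, the exclusion has the same wording as in the SAP table, and ITT is "All randomized participants analyzed according to the treatment group allocated by randomization". Protocol Section 6.3 likewise defines a randomised participant by IRT allocation, whether or not treatment was given.

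The paragraph directly below SAP Table 3 then states: "Participants exposed to study intervention before or without being randomized will not be considered randomized and will not be included in any analysis population". Its next sentence says that these participants' safety experience will be reported separately.

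SAP Section 5.4 opens a rule with "If a participant receives IMP prior to the randomization by mistake, the reference date of efficacy assessment" and makes that date the participant's first IMP administration.

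**The concern.** The paragraph is wider than the table row it sits under in two ways. It adds *before* to *without*, and it extends the exclusion from efficacy populations to every analysis population. The second change alone does nothing, because the safety, PK and ADA populations already require random assignment. The first change matters. People never randomised are already covered by *without*, so *before* can only add people who were dosed first and randomised afterwards.

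Such a participant is in Randomized, ITT and Safety under SAP Table 3 and protocol Table 6, and in no population under the next paragraph. At stake are the denominator of the primary CMH test and of the safety tables, and the principle that nobody allocated by IRT is removed from ITT for an error in the order of dosing. Section 5.2 of the SAP (changes to protocol-planned analyses) does not declare the departure. It refers to the protocol's amendment summary, which lists no change to Section 9.3.

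**Working it through.** **1. Text comparison for a participant dosed by mistake and then allocated by IRT**

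| Source | Randomized / ITT | Safety |
|---|---|---|
| Protocol Table 6 and Section 6.3 | In | In |
| SAP Table 3 | In | In |
| SAP Section 3, paragraph under Table 3 | Out | Out |

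Three other SAP passages fit the table better than the paragraph:
- Section 5.4 gives this participant an efficacy reference date.
- Section 4.7 gives, as its example of someone outside the safety population, a participant who was dosed but not randomised. It is an example, not a complete list.
- Section 4.2 plans a count of participants exposed and not randomised, and no count of those dosed first and then randomised.

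**2. Size of one case**

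1/78 = 1.3% of ITT; 1/39 = 2.6% of an arm.

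**3. Effect on power**

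No figure in the plan is challenged here. The stated 39 per group at 90% power cannot be reproduced because both response rates are redacted. Under the SAP's test (unpooled Z, two-sided 1%), power = Φ(|p1 − p2| / √[p1(1 − p1)/n1 + p2(1 − p2)/n2] − 2.576). With 10% dropout, 35 evaluable per group corresponds to 35/0.9 = 38.9, that is 39 randomised. Assume 10% v 48%, one pair that fits:
- 35 v 35: 0.38/√(0.09/35 + 0.2496/35) − 2.576 = 1.28, power 0.900.
- 34 placebo v 35: 0.38/√(0.09/34 + 0.2496/35) − 2.576 = 1.27, power 0.897.

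Across assumed pairs that give 39 per group (5% v 40%, 10% v 48%, 15% v 55%, 25% v 67%, 30% v 72%), removing one evaluable placebo participant costs about 0.2 to 0.5 percentage points.

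**4. Effect on a result near the threshold**

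The counts are assumed and were chosen to lie close to 0.01. For a negatives of n1 on dupilumab, with m negatives among N in total, the unstratified Mantel-Haenszel statistic is X² = (a − m·n1/N)² / [n1·n2·m(N − m)/(N²(N − 1))]. For 19/39 v 8/39: m = 27, expected 13.5, variance 27 × 51/(4 × 77) = 4.471, X² = 5.5²/4.471 = 6.77, p = 0.0093.

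| Participant removed | Placebo v dupilumab | X² | p |
|---|---|---|---|
| None | 8/39 v 19/39 | 6.77 | 0.0093 |
| Dupilumab responder | 8/39 v 18/38 | 6.13 | 0.0133 |
| Placebo non-responder | 8/38 v 19/39 | 6.39 | 0.0115 |
| Dupilumab non-responder | 8/39 v 19/38 | 7.25 | 0.0071 |
| Placebo responder | 7/38 v 19/39 | 7.80 | 0.0052 |

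From this start, p rises above 0.01 in two of the four removals and falls in the other two. A start just above the threshold can cross the other way. For 9/39 v 20/39, X² = 5.5²/(29 × 49/(4 × 77)) = 30.25/4.614 = 6.56, p = 0.0105. Removing one dupilumab non-responder (9/39 v 20/38) gives X² = 7.07, p = 0.0079.

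**The case against.** The strongest reply is that the event is almost excluded by design. Allocation and kits run centrally through the IRT (protocol Section 6.3), and the first dose is given at the study center (protocol Section 6.1.1). A kit would have to be used outside that process, and nothing in the documents suggests that this happened. This stands, and it limits the weight of the point.

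Three stronger readings are tempting, and the documents do not support them:
- *Safety data would be lost.* They would not. SAP Section 3 and Section 4.7 both provide for separate reporting. The participant leaves the denominators, not the report.
- *Section 5.4 is a second population rule that gives a different N.* It is a date convention and sets no population. It shows that the authors expected to handle such a participant in the efficacy data, but the conflict over N lies within Section 3, between Table 3 and the paragraph below it. If dosing and randomisation fall on the same day, the convention changes nothing.
- *No rule is prespecified, so the choice is left open until a case occurs.* Section 3 does state a rule in advance. The fault is that the rule contradicts the table above it and the protocol, and the SAP does not say which governs.

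The p-values also deserve caution. They ignore the planned stratification by region and background antihistamine use, and they matter only for a result that is already close to 0.01.

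**Conclusion.** The inconsistency is real and minor. It concerns the single word *before*; the exclusion of people never randomised agrees with the protocol and should stay. Applied literally, the paragraph removes an allocated participant from ITT and from the safety, PK and ADA populations because of the order of dosing, which departs from the all-randomised ITT set in both documents.

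Each case would be 1.3% of the planned 78. The effect on power is a fraction of a percentage point under assumed rates. One removal could decide the primary test only if the result lay next to the threshold, and it could help or hurt either arm. The case for correcting the text rests on a clear contradiction and a very cheap repair, not on any expected bias.

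**What to change.** In the paragraph under SAP Table 3, delete *before or*, so that the exclusion covers only participants who were never randomised. Add one sentence: any participant allocated by IRT stays in ITT as randomised, and in the safety population if dosed, even if the first dose preceded randomisation; the SAP Section 5.4 reference date applies and the event is recorded as a protocol deviation. Make the change before database lock and unblinding.

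The cost is two words removed and one sentence added. No new data, analysis or protocol amendment is needed, since the change brings the SAP back to protocol Table 6.

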4 STATISTICAL ANALYSES

4.1 GENERAL CONSIDERATIONS

This SAP provides a comprehensive and detailed description of strategy and statistical techniques for the summary and analysis of EFC16720.

In general, continuous data will be summarized using the number of observations available, mean, standard deviation (SD), median, minimum, and maximum. Categorical and ordinal data will be summarized using the count and percentage of participants.

The baseline value of efficacy parameters is defined as the last available value up to randomization date and prior to the first dose of study intervention unless otherwise specified. The baseline value of the other parameters is defined as the last available value prior to the first dose of investigational medicinal product (IMP) if the participant is treated, or the last available value up to randomization date if the participant is not exposed to IMP.

Observation period

The observation period will be divided into 4 segments:

- The **pre-treatment period** is defined as the period up to first IMP administration.
- The **treatment-emergent (TE) period** is defined as the period from the first IMP administration to the last IMP administration + 98 days. The treatment-emergent period includes the following 2 periods:
 - The **on-treatment period** is defined as the period from the first IMP administration to the last administration of the IMP + 14 days
 - The **residual treatment period** is defined as the period from the end of the on-treatment period to the end of the treatment-emergent period.
- The **post-treatment period** is defined as the period from the end of the treatment-emergent period.

The on-study period is defined as the time from start of intervention until the end of the study defined as the status date collected on e-CRF page “Completion of End of Study”.

4.2 PARTICIPANT DISPOSITIONS

The number (%) of participants included in each of the analysis populations listed in [Table 3](#) will be summarized.

Screen failures are defined as participants who consent to participate in the study but are not subsequently randomized. The number (%) of screen failures and reasons for screen failures will be provided in the screened population.

The number (%) of participants in the following categories will be provided:

- Randomized participants
- Randomized but not exposed participants
- Randomized and exposed participants
- Participants who completed the study intervention period as per protocol
- Participants who did not complete the study intervention period as per protocol and main reason for permanent intervention discontinuation including due to COVID-19 pandemic.
- Participants who completed the study period as per protocol
- Participants who did not complete the study period as per protocol and main reason for study discontinuation including due to COVID-19 pandemic.
- Vital status at last study contact

The number of exposed and not randomized participants will also be summarized.

Protocol deviations

Critical and major protocol deviations (automatic or manual) will be summarized in the randomized population and according to COVID-19 impact (i.e., deviations related to COVID-19 pandemic and deviations not related to COVID-19 pandemic). In addition, deviations potentially impacting the primary endpoint analysis may be summarized.

4.3 PRIMARY ENDPOINT(S) ANALYSIS

4.3.1 Definition of endpoint(s)

The primary endpoint is the proportion of participants with negative ice cube provocation test (absence of a confluent hive/wheal at the entire skin site of exposure) at Week 24.

4.3.2 Main analytical approach

The primary analysis population for the efficacy endpoints will be the ITT population. The statistical hypotheses for comparing dupilumab against placebo on the primary endpoint of proportion of participants with negative ice cube provocation test at Week 24:

- Null hypothesis H0: No treatment difference between dupilumab and placebo.
- Alternative hypothesis H1: There is a treatment difference between dupilumab and placebo.

For efficacy analysis, [Table 4](#) presents the highly influential prohibited medications and highly influential rescue medications which will be considered as intercurrent events if the last column indicates as “Yes” and confirmed through blinded medical review and therefore will be handled in the estimands for endpoints defined in [Table 2](#). Blinded medical review of participants who received the medications listed in [Table 4](#) will be implemented before database lock to ensure the medication use was due to treatment failure instead of an unrelated condition.

Table 4 - Highly influential prohibited medications and/or highly influential rescue medications impact on efficacy

Medication	Comment	Highly influential (Yes/No) ^a / Selection criteria
Systemic immunosuppressants (immunosuppressive/immunomodulating drugs) e.g., systemic corticosteroids (oral or parenteral [intravenous, intramuscular, SC]), cyclosporine, mycophenolate-mofetil, interferon gamma, Janus kinase inhibitors, azathioprine, methotrexate, hydroxychloroquine, dapsone, sulfasalazine, colchicine, etc.	IMP to be discontinued	Yes (Standardized drug groupings (SDGs) Other immunosuppressants, tumour necrosis factor (TNF) alpha inhibitors, Calcineurin inhibitors, Interleukin inhibitors, Selective immunosuppressants – all Narrow)
Any cell-depleting agents including but not limited to rituximab		Yes (CDG10236 Cell depletion agents)
Other monoclonal antibodies (which are biological response modifiers) including anti-IgE therapy (omalizumab).		Yes (SDG Monoclonal antibodies Narrow)
IVIG		Yes (CDG00488 Intravenous immunoglobulin therapy - See Section 5.5)
Plasmapheresis		Yes (CMQ00079 based on the following PTs: Plasmapheresis, Apheresis)
Other investigational drugs.		No, except ones with mechanism of action that may impact efficacy
Topical corticosteroids.	No IMP discontinuation	No
Topical calcineurin inhibitors.		No
Topical and oral antihistamines (other than those allowed as background therapy).		No
Routine doses of doxepin (daily or every other day during 5 or more consecutive days).		No
LTRAs and H2 receptor antagonists, unless stable and taken for diseases other than chronic inducible ColdU.		Yes for LTRAs; No for H2 receptor antagonists (SDG Leukotriene receptor antagonists for obstructive airway diseases Narrow)
Antifibrinolytic tranexamic acid and epsilon-aminocaproic acid		No
Phototherapy, including tanning beds.		No
Additional H1-AH up to 4-fold (2-fold in Japan)	No IMP discontinuation	No
Corticosteroids		Yes (SDG Corticosteroids Narrow excluding where Route is Topical, Nasal, Respiratory (Inhalation) or Ophthalmic)

a When yes, if confirmed through blinded medical review that the medication use was due to treatment failure instead of an unrelated condition, the estimand for the intercurrent event handling strategy will be as follows: composite for continuous and responder endpoints. Otherwise, a treatment policy strategy will be applied.

The intercurrent event handling strategy for the primary estimand is the treatment policy/composite approach.

The primary efficacy endpoint will be analyzed using the Cochran-Mantel-Haenszel test stratified by region (combined countries) and background H1-antihistamine regular/daily use (Yes/No). The comparison of the proportions of participants with negative ice cube provocation test at Week 24 between dupilumab and placebo will be derived, and the corresponding odd ratios and the 95% confidence interval (CI) will be reported. Participants who receive highly influential prohibited medications and/or highly influential rescue medications (see [Table 4](#)) will be considered as having positive ice cube provocation tests for time points after the medication usage. For other participants, all available data including those collected during the off-treatment period will be used to determine the positive/negative ice cube provocation test outcome. Participants with missing ice cube provocation test data at Week 24 will be considered as having positive ice cube provocation tests.

The following is a sample code for the primary analysis.

```
proc freq data=dataice;  
  tables region*background*trtgrp*response/relrisk cmh;  
  weight Count;  
run;
```

